### 2. Concomitant medication (CM) start and end date imputation

The imputation of missing medication start and/or end dates is performed for the following reasons:

- To determine if a medication is a prior medication or a concomitant medication.
- To determine if treatment with the medication satisfies any of the medication-related exclusion criteria #16, #17, #18, #19, #20, #21, #22, #23, #24 and #26 for subject eligibility.

The imputation conventions described below for concomitant medication also apply to concomitant procedure (CP).

The medication start and end dates are separated into 3 different data fields, including day, month, and year. Completely missing medication start and/or end date (i.e., missing day, missing month, and missing year) will not be imputed. Partially missing medication start/end date will be imputed according to treatment start date. The rules on how to determine if a medication is a

prior medication only or both prior and concomitant medication and to determine if subjects violated any protocol specified medication-related exclusion criteria are specified below.

The prior and concomitant medications data listings will display all data as collected; imputed values will not be shown.

- **Medication Start Date Imputation**

- a) If medication start year is missing, then no imputation
- b) If medication start year is reported while medication start month and day are missing, then medication start month/day = '01JAN'
- c) If medication start year and month are reported while medication start day is missing, then medication start day = '01'

- **Medication End Date Imputation**

- a) If medication start date and medication end date are completely missing; or medication end date is completely missing while medication start date is either a complete date or partially missing and the observed/imputed medication start date < treatment start date, then no imputation:
  - If Ongoing = Yes, the medication is considered to be both prior and concomitant medication
  - If Ongoing = No or missing, the medication is considered to be a prior medication only
  - Subject will be considered as violating the medication-related exclusion criteria if the medication is one of the prohibited medications according to the medication-related exclusion criteria.
- b) If medication start date is completely missing while medication end date is partially missing; or medication end date is partially missing while medication start date is either a complete date or partially missing and the observed/imputed medication start date < treatment start date, then the missing medication end date will be imputed as follows:

	MMM Missing	MMM < TRT Month	MMM = TRT Month	MMM > TRT Month
YYYY < TRT Year	31DEC	Last day of MMM	Last day of MMM	Last day of MMM
YYYY = TRT Year	TRTDT *	Last day of MMM	TRTDT *	01MMM
YYYY > TRT Year	31JAN	Last day of MMM	Last day of MMM	Last day of MMM

\* If Ongoing = Yes, then no imputation.

Where: YYYY = Medication end year; MMM = Medication end month; TRT Year = Treatment start year; TRT Month = Treatment start month; and TRTDT = Treatment start date.

- The observed and/or imputed medication end date will be used to determine if a medication is a prior medication only; or is both a prior and a concomitant medication.
- If the medication is one of the prohibited medications according to the medication-related exclusion criteria, the observed and/or imputed medication end date will also be used to determine if a subject meets any medication-related exclusion criteria.

c) If the medication start date is either a complete date or partially missing with the observed/imputed medication start date  $\geq$  treatment start date, then no imputation for medication end date, and:

- The medication is considered to be a concomitant medication only.
- Subject doesn't meet any medication-related exclusion criteria.

### **3. Other date imputations**

Any event with a partial date that requires imputation but has no specific imputation rule will be imputed as follows:

- If the day is missing, then impute the day as '01'
- If the month is missing, then impute the month as 'JUL'
- If the imputation of a start date causes the start date to be post the non-missing end date, then the start date will be imputed as the end date.
- If the imputation of a start date causes the start date to be prior to the start of treatment (but the event should happen post-baseline), then the start date will be imputed as "treatment start date + 1."
- Any date cannot be imputed past the date of death. When this happens, the date will be imputed as the date of death.

**Appendix B. Algorithm to Identify Critical Protocol Deviations that Exclude Subjects from the Per-Protocol (PP) Population**

The below algorithm outlines the criteria for identifying critical protocol deviations. Subjects with at least one of these critical protocol deviations will be excluded from the PP population.

- A. Deviations of subject eligibility (Inclusion/Exclusion criteria) that will result in exclusion from PP population (refer to the protocol for the complete text of each inclusion/exclusion criterion below):
  - 1. Inclusion Criterion #2: Less than 5 years postmenopausal.
  - 2. Inclusion Criterion #3: A BMD T-score outside the required range or fracture criteria not met.
  - 3. Exclusion Criterion #1: History of more than 4 spine fractures, mild or moderate, or any severe fractures.
  - 4. Exclusion Criterion #2: Presence of abnormalities of the lumbar spine that would prohibit assessment of spinal bone mineral density (BMD).
  - 5. Exclusion Criterion #3: Unevaluable hip BMD or subjects who have undergone bilateral hip replacement.
  - 6. Exclusion Criteria #4, #5, #6: Diseases and treatments affecting bone strength.
  - 7. Inclusion Criterion #5: Laboratory tests affecting the bone strength.
  - 8. Exclusion Criteria #16, #17, #18, #19, #20, #21, #22, #23, #24 and #26: Prior treatment with bone-acting agents within the specified time periods.
- B. Deviations of study drug administration that will result in exclusion from PP population:
  - 1. Duration of study drug exposure is less than 3 months (90 days)
  - 2. Compliance to study drug administration < 80%
- C. Deviations of efficacy measurements that will result in exclusion from PP population:
  - 1. Lumbar spine BMD is missing at baseline
  - 2. No post-baseline lumbar spine BMD assessments recorded
- D. Other critical protocol deviations
  - 1. Any protocol deviation with potential major impact on the efficacy endpoint will exclude a subject from the PP population. This will include subjects taking any prohibited medications during study.

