#### **4.6.2. Adverse Events of Special Interest**

An adverse event of special interest (AESI) is an AE that is designated to be of special medical or scientific interest to the Sponsor. There are four major categories of AESIs as follows:

- Administration site reaction AEs -- Skin reaction AEs at the injection/application site
- Skin AESIs -- AEs of eschar, ulcer, or non-healing wounds at the injection/application site
- Hypersensitivity AESIs -- TEAEs in the Hypersensitivity Standardized MedDRA Query (SMQ narrow)
- Other AESIs:
  - Orthostatic hypotension
  - Tachycardia
  - Nausea
  - Hypercalcemia
  - Hypercalciuria
  - Hypophosphataemia

The MedDRA PTs, High Level Terms (HLT), and SMQs used to identify the AESIs are stored in the study folder in the Biometrics SAS environment.

An overall summary of the treatment emergent AESIs will be provided, in which the number of subjects with any adverse events, number of subjects with any TEAEs, number of subjects with any treatment-related TEAEs, number of subjects with any severe TEAEs, number of subjects with any treatment-related severe TEAEs, number of subjects with any serious TEAEs, number of subjects with any treatment-related serious TEAEs, number of subjects with any TEAEs leading to study drug withdrawal, number of subjects with any TEAEs leading to study drug interruption, number of subjects with any TEAEs leading to study discontinuation, number of subjects with any TEAEs related to the device, and number of subjects with any TEAEs leading to death will be summarized by treatment group and overall.

The treatment emergent AESIs will be summarized by PT and SOC for each of the AESIs. Summary of the onset time and duration of the treatment emergent AESIs will be provided by

treatment group using descriptive statistics (number of subjects, mean, SD, median, interquartile range, minimum and maximum).

AESI onset time groups include:

- 1 day
- 2-3 days
- 4-7 days
- 8-15 days
- 16-29 days
- 1 to <2 months
- 2 to <6 months
- 6 to <10 months
- $\geq$ 10 months

AESI duration groups include:

- For Administration site reaction AEs, Skin AESI and Hypersensitivity AESIs:
  - < 1 hour
  - 1-<2 hours
  - 2-<4 hours
  - 4-<24 hours
  - 1-<2 day
  - 2-3 days
  - 4-7 days
  - 8-15 days
  - 16-29 days
  - >29 days
- For other AESIs:
  - 1-<2 day
  - 2-3 days
  - 4-7 days
  - 8-15 days
  - 16-29 days
  - >29 days

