For AESI duration, if there is more than one occurrence of the AESI for a subject, then the average duration for all occurrences for the subject will be used. If AE stop date is missing, then the last study date will be used. If both AE start date and AE stop date are missing, the AE duration will be missing.

To evaluate the relationship between AESIs and the antibody status, the incidence of treatment emergent AESIs will also be summarized by antibody status (ADA-, ADA+/Nab+, ADA+/Nab-, All ADA+, and Overall), SOC, and PT for both treatment groups.

An overall summary of the treatment emergent AESIs, as described above, will also be presented by treatment group (and overall) for the following subgroups:

- Age group (< 65, 65 - < 75, and  $\geq$  75 years)
- BMI group (BMI < 25,  $25 \leq$  BMI < 30, and BMI  $\geq$  30)
- Region (North America and Europe)

Subject listings will be provided for each of the AESIs.

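### The SAP has no specific rule for a partial AE stop date, and either rule that could be applied gives wrong AESI durations

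*SAP*

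**What the plan says.** SAP section 4.6.2 plans a duration output for each AESI: "Summary of the onset time and duration of the treatment emergent AESIs will be provided". Duration categories for administration-site, skin and hypersensitivity events run from under 1 hour to over 29 days. With repeated occurrences, "the average duration for all occurrences for the subject will be used". On stop dates the section says only: "If AE stop date is missing, then the last study date will be used".

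Appendix A, section 1, deals with AE start dates. Section 2 deals with medications, and by extension procedures. Section 3 is the catch-all: "Any event with a partial date that requires imputation but has no specific imputation rule will be imputed as follows". Its two imputation lines are "If the day is missing, then impute the day as '01" and "If the month is missing, then impute the month as 'JUL". Of its two order checks, one begins "If the imputation of a start date causes the start date to be post the non-missing end date" and the other concerns an imputed start that falls before treatment. The only remaining limit is the date of death.

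**The concern.** A stop date with an unknown day, or an unknown day and month, has to be completed before duration can be calculated. Taken at its word, the catch-all picks the earliest day of the month for an end date. Any event that began after the first of the month in which it ended then stops before it starts, and no check catches this. Section 4.6.2 offers a second candidate, the last study date, but does not say whether a partial date counts as missing.

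The persistence of local reactions is part of the safety description of the new patch. If the rule is left open, programmers will probably notice negative durations when the tables are run. They would then choose a remedy after database lock, when the blinding of analysis staff described in SAP section 1.2.3 has ended.

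**Working it through.** The plan gives no figure on this point, so there is none to reproduce. The two candidate rules can be compared directly.

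**Assumptions.** Duration = stop − onset + 1 in days; the SAP uses this form for drug exposure but does not state it for AESIs. Onset is equally likely on each of the 366 days of 2020. True duration is D days.

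**Reading A: catch-all, only the day unknown.** The stop moves to the first of its month. It stays on or after onset only if a first-of-month falls within the event. For D up to 29, that is D onset dates for each of 12 months, so

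share with stop before onset = (366 − 12D)/366.

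The stop moves back by its day of the month minus 1. With 7 months of 31 days, 4 of 30 and one of 29, the mean shift is (7×31×15 + 4×30×14.5 + 29×14)/366 = 5401/366 = 14.8 days. The mean imputed duration is therefore D − 14.8.

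| True duration D | Share with stop before onset | Mean imputed duration (days) |
|---|---|---|
| 1 | 354/366 = 96.7% | −13.8 |
| 3 | 330/366 = 90.2% | −11.8 |
| 5 | 306/366 = 83.6% | −9.8 |
| 7 | 282/366 = 77.0% | −7.8 |
| 10 | 246/366 = 67.2% | −4.8 |
| 15 | 186/366 = 50.8% | 0.2 |
| 20 | 126/366 = 34.4% | 5.2 |
| 29 | 18/366 = 4.9% | 14.2 |

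On this reading the imputed stop is never later than the true stop.

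*Example.* Onset is 10 March and the true stop 14 March, recorded as March with the day unknown. The imputed stop is 1 March, so duration = 1 − 10 + 1 = −8 days instead of 5. If the subject also had a fully dated 5-day reaction, her average would be (5 − 8)/2 = −1.5 days instead of 5.

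**Reading B: catch-all, day and month unknown.** The stop becomes 1 July of the stop year. For events of 1 to 7 days, 48% to 50% get a stop before onset, and 49.7% get a duration longer than the true one. The error has no single direction.

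**Reading C: section 4.6.2 taken to cover partial dates.** The stop becomes the last study date, assumed here to be Day 390 (12 + 1 months of 30 days). With onset uniform over Days 1 to 360, duration = 390 − onset + 1. It averages 210.5 days and ranges from 31 to 390. Every such event falls in the over-29-days category, including one known to have ended months earlier.

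**Dilution.** Let f be the share of records with only the stop day missing; the documents do not give f. Under Reading A, about 0.9f of all 1-to-3-day reactions get a stop before onset: 0.9% at f = 1%, 4.5% at 5%, 9% at 10% and 45% at 50%. Mean duration across all records falls by 14.8f days, which is about 0.7 days at f = 5% and 1.5 days at 10%.

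**The case against.** The best counter-argument is that the catch-all does not govern at all. It covers only dates without a specific rule, and section 4.6.2 has a stop-date rule written for AESI duration. SAP sections 3.11 and 4.6.1 also speak loosely of missing dates when they send the reader to Appendix A rules that handle partial ones. Against this, Appendix A distinguishes completely missing from partial dates, so both readings are open. The objection stands as far as the direction of bias goes: one cannot say the plan makes durations too short. It does not remove the problem, because Reading C is also wrong.

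It can also be argued that partial stop dates will be rare. The protocol has daily symptom diaries (6.6.3.2), 24-hourly evaluation of severe reactions (6.6.3.1), serial photographs of skin AESIs (7.1.3.1) and data queries (9.7). This is fair, and the documents neither confirm nor exclude it.

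Nor is the medication end-date table in Appendix A a clean precedent for an end-of-month rule. Many cells read "Last day of MMM", but others give the first of the month, the treatment start date or 31 January, and 31 December applies only when the end year precedes the treatment year. Medications started on treatment get no end-date imputation. The table's stated purposes are classification and eligibility, not duration.

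A reader might go on to infer that most short skin reactions receive a stop before onset. That is true only among records with a missing stop day; for 1-to-3-day reactions overall it would need f above about 0.5/0.9 = 56%. A reader might also infer that the error favours the patch, or that negative values land in the under-1-hour category. Nothing in the documents shows more partial stop dates in the patch arm, and the SAP does not say how negative durations would be categorised.

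**Conclusion.** The gap is real. The SAP has no specific rule for partial AE stop dates, and neither rule that might fill it gives sensible durations. Read literally, the catch-all puts the stop before onset in about 84% of 5-day, 67% of 10-day and 34% of 20-day events **whose stop day is unknown**, given uniform onset. Read the other way, section 4.6.2 turns the same events into durations of a month to over a year, about 210 days on average under the assumed last study day. The net direction of bias cannot be stated, and its overall size depends on a share of partial dates that the documents do not give.

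The consequence is confined to descriptive AESI duration summaries. AESI incidence, severity and relationship to treatment, and the primary endpoint, do not depend on the stop date. This is worth correcting because the correction is simple and is better fixed in advance than chosen with treatment known.

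**What to change.** Add an AE stop-date rule to Appendix A:

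- The last-study-date rule in section 4.6.2 applies only when the stop date is completely missing.
- If only the day is unknown, impute the last day of the known month. If the month is also unknown, impute the last day of the known year.
- Cap the result at the last study date and the date of death.
- Never set the stop before the observed or imputed onset.

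This costs one rule and a few lines of code, with no change to data collection. The downside is that durations of affected records may be overstated, by up to about a month when only the day is missing and by more when the month is missing, subject to the caps. For a safety summary that is the more cautious direction, but it is still a choice. Reporting the number of AESI records with an imputed stop date, by arm, would let readers judge its influence.

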Appendix C. Criteria for Potentially Clinically Significant (PCS) Laboratory Values

Lab Parameter	Conventional Unit		SI Unit	
	Low	High	Low	High
Hematology				
Absolute Eosinophils		>5000 cells/mm 		>5.00 10  /L
Absolute Lymphocytes	≤499 cells/mm 		≤0.499 10  /L	
Absolute Neutrophils	≤999 cells/mm 		≤0.999 10  /L	
Hemoglobin	≤9.4 gm/dL (female)	change from baseline ≥2.1 g/dL (female)	≤94 g/L (female)	change from baseline ≥21 g/L (female)
Platelets	≤99000 cells/mm 		≤99 10  /L	
White Blood Cells	≤1499 cells/mm 	≥20001 cells/mm 	≤1.499 10  /L	≥20.0 10  /L
Activated Partial Thromboplastin Time		≥1.41*ULN		≥1.41*ULN
Prothrombin Time		≥1.21*ULN		≥1.21*ULN
Serum Chemistry				
Alanine Aminotransferase		≥5.1*ULN		≥5.1*ULN
Albumin	<2.5 g/dL		<25 g/L	
Alkaline Phosphatase IFCC		≥3.1*ULN		≥3.1*ULN
Aspartate Aminotransferase		≥5.1*ULN		≥5.1*ULN
Bilirubin		≥1.51*ULN (with ALT and/or AST>ULN)  ≥2.0*ULN (with normal liver function tests)		≥1.51*ULN (with ALT and/or AST>ULN)  ≥2.0*ULN (with normal liver function tests)
Calcium	≤7.4 mg/dL	≥11.6 mg/dL	≤1.85 mmol/L	≥2.9 mmol/L
Cholesterol Total		>226 mg/dL		>5.8534 mmol/L
Creatine Kinase		≥3.1*ULN		≥3.1*ULN
Creatinine		≥2.1 mg/dL		≥ 185.64 umol/L
Glucose	≤54 mg/dL	>200 mg/dL (random)	≤ 2.997 mmol/L	> 11.1 mmol/L
Phosphorus	<2.0 mg/dL	>5.0 mg/dL	<0.645 mmol/L	>1.613 mmol/L
Potassium	≤3.2 mEq/L	≥5.5 mEq/L	≤3.2 mmol/L	≥5.5 mmol/L
Protein Total	<5 g/dL		<50 g/L	
Sodium	≤129 mEq/L	≥148 mEq/L	≤129 mmol/L	≥148 mmol/L
Urine				
Glucose		2+ (≥100 mg/dL)		2+ (≥5.55 mmol/L)
Protein		2+ (≥100 mg/dL)		2+ (≥ 1.0 gm/L)
Blood		>50 rbc/hpf		>50 rbc/hpf
Source: FDA Guidance for Industry 2007, Toxicity Grading Scale for Health Adult and Adolescent Volunteers Enrolled in Preventive Vaccine Clinical Trials				

## Appendix D. Normalization of Clinical Laboratory Values

Because normal values of laboratory parameters in this study were provided from different local or central laboratories with inconsistent units and normal ranges, all numerical values will be converted to the Standard International (SI) units and normalized to a standard set of reference/normal ranges as described by Chuang-Stein (1992 and 2001). The normalization process will be performed separately for each of the laboratory parameters.

For numerical laboratory values, the normalized values will be proportional to the ratio of the widths of reference ranges and aligned with the corresponding lower limits. For example, let  $(L_s, U_s)$  denote the standard reference range, which is the Medpace normal ranges in this study. Let  $(L_A, U_A)$  represents the reference range from a central or local Laboratory  $A$ . Let  $\varphi$  denote the laboratory value provided from Laboratory  $A$ , which is needed to be normalized. The normalized value,  $\varphi_s$ , can be derived from the formula,

$$\varphi_s = L_s + \beta \times (\varphi - L_A),$$

[figure not shown]
where  $\beta = (U_s - L_s) / (U_A - L_A)$  equals the ratio of the widths of the reference ranges.

If the normalized value,  $\varphi_s$ , becomes negative, the value will be replaced by zero. If one, say the lower, of the limits of a reference range is missing then the missing limit will be imputed according to the ratio of the limits from one of the closest reference ranges provided in this study. For example, let  $L_M$  denote the missing lower limits from Laboratory  $M$ . Its corresponding higher limit,  $U_M$ , is found to be closest to the upper limit,  $U_C$  from Laboratory  $C$  among all the reference upper limits in the study. Then,  $L_M$  will be imputed by the formula,

$$L_M = L_C \times (U_M / U_C),$$

where  $L_C$  denotes the lower limit from Laboratory  $C$ . For cases where only the upper limits are missing (i.e., the lower ones are non-missing), same imputation process will be performed. For cases where both limits of a reference range are missing, the missing upper and lower limits will be imputed by the largest upper and lowest lower limit among all the observed reference ranges, respectively.

Signature Page for RAD-CLIN-002892 v1.0

Approval	
	17-Sep-2021 15:59:22 GMT+0000

Approval	
	17-Sep-2021 16:22:11 GMT+0000

Approval	
	20-Sep-2021 18:16:50 GMT+0000

Signature Page for RAD-CLIN-002892 v1.0
